5.5 Replacement of individual subjects after

withdrawal Not applicable.

5.6 Follow-up of subjects withdrawn from treatment

Patients who drop-out out of (part of) the treatment remain in the study and will still be asked to complete the follow-up measures. Priority will be given to the online assessment with the PCL-5 and OQ-45.

5.7 Premature termination of the study

There are no criteria, other than mentioned under section 6, for a premature termination of the study.

6. SAFETY REPORTING

6.1 Section 10 WMO event

This study will be performed according to the Declaration of Helsinki (64th WMA general assembly; October 2013) and the International Conference on Harmonisation – Good Clinical Practice (ICH-GCP). The definitions of adverse events and serious adverse events described in these guidelines will be used for the present study.

In accordance to section 10, subsection 1, of the WMO, the investigator will inform the subjects and the reviewing accredited Ethical Review Board (ERB) if anything occurs, on the basis of which it appears that the disadvantages of participation may be significantly greater than was foreseen in the research proposal. The study will be suspended pending further review by the accredited ERB, except insofar as suspension would jeopardise the subjects' health. The investigator will take care that all subjects are kept informed.

Subjects are entitled to get information and to ask questions, before, during and after being part of the research to the researchers. Apart from the provided information, there is an independent expert involved. He can provide information for patients, but is not involved in this study himself. In this study the independent expert is a psychiatrist working in one of the companies within Arkin, named Mentrum. He is not involved in the Sinai Center.

6.2 AEs, SAEs and SUSARs

6.2.1 Adverse events (AEs)

Adverse events are defined as any undesirable experience occurring to a subject during the study, whether or not considered related to the study. All adverse events reported by the subject or observed by the investigator or his staff will be recorded.

6.2.2. Serious adverse events (SAEs)

We do not expect any serious adverse event (i.e. any untoward medical occurrence or effect that results in death; is life threatening (at the time of the event); requires hospitalisation or prolongation of existing hospitalisation; results in persistent or significant disability or incapacity; is a congenital anomaly or birth defect; any other important medical event that may not result in death, be life threatening, or require hospitalization, may be considered a serious adverse experience when, based upon appropriate medical judgement, the event may jeopardize the subject or may require an intervention to prevent one of the outcomes listed above). The main reason for this is that all four treatments given in the RCTs are evidence-based for at least one of the disorders the patients suffer from (PTSD and PD) and patients who will be assigned to the PTSD-treatment only can given PD-treatment as well after T4 (after 6-12 months) within the research design.

Suicidality or self-injurious behaviour is very common in the study population included for this study. It is also known that starting a new treatment, such as EMDR or DBT could increase symptoms in the beginning, which can develop into suicidal behaviour. SAE's which will occur during the treatment and for which medical care is needed, will be reported to the accredited METC. To monitor the SAE's, patients will be asked to fill in a self-injury questionnaire (*Opzettelijk zelfverwondend gedrag, Baetens & Claes 2014 based on The Brief Non-Suicidal Self-Injury Assessment Tool (BNSSI-AT) van Janis Whitlock en Amanda Purington (2013)*) at the regular assessments. In case of SAE's for which medical care is needed, in between the assessments, therapists will report these incidents to the researchers at the weekly consultations, whom will report these to the accredited METC. The sponsor will report SAEs to the accredited METC that approved the protocol, within 7 days of first knowledge for SAEs that result in death or are life threatening followed by a period of maximum of 8 days to complete the initial preliminary report. All other SAEs will be reported within a period of maximum 15 days after the sponsor has first knowledge of the serious adverse events.

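### Section 6.2.2 words the SAE reporting route more narrowly than the sponsor's own duty to report, by adding a medical-care condition and a during-treatment condition that the final rule does not carry

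*Combined protocol and SAP*

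**What the plan says.** Section 6.1 takes its definitions from the Declaration of Helsinki and ICH-GCP: "The definitions of adverse events and serious adverse events described in these guidelines will be used for the present study". Section 6.2.2 then lists six seriousness criteria: death, threat to life, hospitalisation, lasting disability, congenital anomaly, and other important medical events. None of them depends on medical care or on being in treatment.

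The same section describes reporting in three places:

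- A general sentence, confined to SAEs that arise while the patient is in treatment: such events "for which medical care is needed, will be reported to the accredited METC".
- A route for events that arise between study assessments, again confined to SAEs that need medical care. Here "therapists will report these incidents to the researchers at the weekly consultations", and the researchers then inform the METC.
- A closing sponsor rule: "The sponsor will report SAEs to the accredited METC that approved the protocol, within 7 days of first knowledge" where the event is fatal or life-threatening, and at most 15 days for all other SAEs.

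The section also uses a patient-completed self-injury questionnaire at the regular assessments to monitor SAEs. Section 6.4 states that SAE reporting runs to the end of the study, which section 9.5 defines as the last visit of the last patient.

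**The concern.** The first two sentences carry a medical-care condition and the sponsor rule does not. The first sentence is also confined to the treatment period, which section 6.4 does not do. Staff following different sentences of one section could reach different decisions about the same event.

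This matters because both sponsor deadlines run from the day the sponsor learns of the event, so the route that brings the news determines when the clock starts. Section 6.2.2 calls suicidality and self-injury very common in this population and notes that starting a new treatment can increase symptoms. There is no DSMB (section 6.5), no annual safety report (section 6.3) and no interim analysis (section 7.4). The ethics committee is the only outside safety reviewer described. What reaches it should not depend on which sentence a therapist happens to follow.

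**Working it through.** The check is mainly textual, with one short calculation on treatment time. The relevant statements are:

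| Place | Content | Medical-care condition | During-treatment condition |
|---|---|---|---|
| 6.2.1 | All AEs reported by the subject or observed by staff are recorded | No | No |
| 6.2.2, definition | Six seriousness criteria | No | No |
| 6.2.2, general sentence | SAEs go to the METC | Yes | Yes |
| 6.2.2, therapist route | Therapist to researchers to METC | Yes | No |
| 6.2.2, sponsor rule | 7 days, or 15 days for all others | No | No |
| 6.4 | SAEs reported to end of study | No | No |
| 9.4 | SAEs in the annual progress report | No | No |

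**Step 1: conditions against the definition.** The qualified sentences pick out a subset of SAEs. They leave the definition intact, so there is no contradiction at this level.

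**Step 2: conditions against the sponsor rule.** If every SAE needs medical care, the phrase adds nothing. If some do not, the qualified sentences conflict with a rule that covers all SAEs. A patient found dead is the clearest example: the event is serious by the first criterion, and no care is needed. The sponsor rule has no such gap, because its short deadline applies "within 7 days of first knowledge for SAEs that result in death or are life threatening".

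**Step 3: how the sponsor learns of an event.** Section 6.2.2 describes two sources. The therapist route operates between assessments and carries the medical-care condition. The questionnaire is completed by the patient, so it cannot report a death. The notes to Table 1 label it a screener for non-suicidal self-injury, a label that does not cover suicide attempts. Assessments fall at about 0, 3, 6, 9, 12 and 18 months, so the intervals that depend on the therapist route are 3 months long, and 6 months for the last one.

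**Step 4: what the during-treatment condition leaves out.** Inputs: 3 to 6 months of treatment in the trauma-only arms and 12 months in the integrated arms (Summary); follow-up to 18 months (section 3). Assumption: treatment means the allocated treatment.

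- Trauma-only, first 12 months: 12 − 6 = 6 to 12 − 3 = 9 months outside treatment. This reproduces the 6 to 9 month pause stated in the Summary.
- Integrated, first 12 months: 12 − 12 = 0 months.
- To month 18: trauma-only 18 − 6 = 12 to 18 − 3 = 15 months; integrated 18 − 12 = 6 months.

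Two details affect these figures. Section 3 also gives 9 to 12 months for the integrated care path; at 9 months the integrated figures become 12 − 9 = 3 and 18 − 9 = 9. Trauma-only patients may start DBT or SFT after T4, and the text does not say whether that counts as treatment, so the comparison beyond month 12 is uncertain. Within the first year the direction is clear: the literal wording leaves out more time in the trauma-only arms.

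**Step 5: number of events.** The documents give no SAE rates, so no count of affected events can be derived.

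**The case against.** The strongest reply is that the reporting duty is already complete. A reader might infer that a death or life-threatening attempt without medical care escapes METC reporting altogether. The documents do not support that: the 7-day rule names these events without any condition, and the qualified sentences do not say that only such SAEs are passed on.

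The text also speaks of care that is needed, not care that was sought or received. A life-threatening attempt for which nobody sought help still needed care and would pass the condition, and lasting disability ordinarily would too. It is therefore not safe to count how many of the six criteria could be met without care and call that the size of the gap.

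Third, there are other ways for the study team to learn of events. Section 6.2.1 records all AEs that are reported or observed, section 5.4 has the treating physician contact the team about important changes, and section 9.4 reports SAEs yearly. Nothing forbids a therapist from passing on more than the sentence asks. Because of 6.2.1, a reader who infers that events would be lost from the SAE and AE incidences planned in section 7.3 goes further than the text; such loss is possible but not shown. Nor does the protocol rank suicidality as its main risk.

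All of this stands and limits the point. It does not remove the mismatch. Section 6.2.1 concerns recording and sets no time for passing an SAE on. Section 5.4 does not mention SAEs or a time limit. An annual report cannot serve a 7- or 15-day deadline. The between-assessment route written for that purpose in 6.2.2 still carries a condition that the duty lacks.

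**Conclusion.** The point holds as an internal inconsistency that should be corrected. Section 6.2.2 limits its general METC sentence by two conditions and its therapist route by one, while its closing rule and section 6.4 carry neither. The consequence is limited: some SAEs, most clearly a death where no care was needed, fall outside the literal wording of the between-assessment route, so the sponsor may learn of them late or by chance. Once known, they are reportable.

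The number of such events cannot be estimated from the documents. The one quantity available is treatment time: 6 to 9 months of the first year outside treatment in the trauma-only arms, against 0 (or 3, on the shorter duration in section 3) in the integrated arms. This assumes that treatment means the allocated treatment and that the sentence is applied literally. The correction is worth making because it is cheap, the population has frequent suicidality or self-injury, and the ethics committee is the only outside safety reviewer described.

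**What to change.** Reconcile section 6.2.2 with its own closing rule and with section 6.4:

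- Delete the medical-care condition from the general METC sentence and from the therapist-route sentence.
- Delete the during-treatment condition from the general METC sentence. Removing the medical-care phrase alone would leave post-treatment events outside that sentence.
- State that every event meeting the 6.2.2 definition, up to the end of the study, is passed to the researchers and reported under the existing 7- and 15-day rule.
- Record need for medical care as an attribute of each event, so that the information is kept without acting as a filter.

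The cost is the removal of three short phrases, one clarifying sentence and one data field. The downside is a few more SAE reports. The definition, the deadlines and the planned tabulations stay as they are.

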treatment (1.0), the number of persons needed to include is 50 persons per condition to reach for 80% power. Expecting a dropout rate of 25%, we will include 63 persons per arm, for 4 arms a total of 252 adult patients with PTSD and - at least 4 - PD symptoms. Of these patients, 80 next to 40 healthy matched controls will be asked for additional MRI research before and after treatment. In total, 292 persons will be included in this study.

Intervention: In patients with PTSD and BPD: EMDR (3-6 months plus 6-9 months treatment pause) compared to integrated DBT-EMDR (12 months); in patients with PTSD and CPD: ImRs (3-6 months plus 6-9 months treatment pause) compared to integrated ImRs-SFT (12 months).

Main study parameters/endpoints: Primary outcome measure is PTSD symptom severity after 12 months. Secondary outcome measures are PD symptoms (SCID-5-PD), disability (WHODAS), quality of life (EQ-5D-5L) and health costs (Tic-P). At baseline (T₀) and after 12 months (T₄) clinical interviews (CAPS-5, SCID-5-PD dimensional score) and self-rating scales (PCL-5) will be used. After 3 (T₁), 6 (T₂), 9 (T₃), and 18 months (follow-up), questionnaires only will be used. At baseline, candidate predictors will be measured including above mentioned cognitive, affective, relational factors, and hormonal and epigenetic factors. In a subgroup, structural and functional MRI, with resting-state and an emotion processing (face recognition) will be performed.

Nature and extent of the burden and risks associated with participation and benefits:

The burden and risks associated with participation in this study is reasonable. All patients will receive psychotherapy, which is considered to be the most effective treatment for PTSD and PD. There is evidence that all four conditions are therapeutic in patients with PTSD and PD and no evidence yet what condition is more effective. Total time of the six measurements is approximately 5 hours per patient for interviews and 5 hours for questionnaires (see table 3), which are partly part of the routine outcome measurements (ROM). Questionnaires can be filled in at home. On the one hand, extensive clinical interviews and self-rating scales can be felt as disturbing because of fatigue, taken time and emotional burden. On the other hand, patients may feel well recognized by the time taken by specialized clinicians for them. Assessors will be well-trained and work in close

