3. STUDY DESIGN

The design of this study consists of two – connected - RCTs comparing PTSD-treatment to integrated PTSD-PD treatment in patients with PTSD and comorbid PD in a specialized treatment setting (figure 2):

A1. EMDR versus integrated DBT-EMDR, and

A2. ImRs versus integrated SFT- ImRs.

Assessment points are: baseline (T₀), after 3 months (T₁), after trauma treatment has finished, around 6 months (T₂), 3 months after T₂ (T₃), after 12 months (T₄) and at 18 months (follow-up, FU).

PTSD treatments specifically address the troubling memories of the traumatic event and the personal meaning of the event and consist of 12 to 18 sessions in maximum 6 months, and are:

- EMDR (Eye Movement Desensitization and Reprocessing)

EMDR was developed in 1987 by Shapiro (De Jongh & Ten Broeke, 1998). In EMDR the therapist induces a bilateral stimulation once the client has focused the attention on a disturbing image or memory related to the traumatic experience. The bilateral stimulation is induced by the movement of the therapist's fingers in front of the patients face from

the left to the right with the instruction for the client to follow this movement of the hand with the eyes. Attention is drawn to what traumatic memory and the dysfunctional thoughts about it are currently doing with the patient and not to what the patient was thinking during the traumatic experience.

- ImRs (Imagination and Rescripting Therapy) (Arntz et al., 2007, Raabe et al., 2015).

In ImRs, the patient imagines the (onset of a) traumatic experience and subsequently changes the original course of events by imagining different interventions and outcomes, thereby allowing for the change of original schematic representations and cognitions (Hackmann et al., 2011). ImRs implies changing the traumatic imagery in fantasy, to produce a more favourable outcome (without denying the trauma), imagining having control over the situation and being able to act according to one's needs, to express one's feelings and action tendencies. ImRs was hypothesized to alleviate PTSD symptoms as well as change trauma-related beliefs and schemas (e.g. powerlessness, victimization, and inherent badness). It is suggested that ImRs might be more effective in patients with emotions and cognitions like anger, irrational guilt, shame disgust and/or self-contempt (Arntz et al., 2007).

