Integrated PTSD-PD treatment consist of a PTSD treatment interwoven in a PD treatment that takes at least twice sessions per week, for the duration of one year:

- DBT (Dialectical Behavior Treatment), a manualized outpatient cognitive-behavioral treatment with two components: (a) weekly individual therapy and (b) weekly group skills training. Individual sessions focus on a hierarchy of target behaviors, which the patient tracks on a daily basis with diary cards. Behavioral analyses of the pattern and chain of thoughts, emotions, and events take place routinely to help the patient identify triggers and alternative strategies for coping. Change strategies such as problem solving and reinforcement techniques are used in combination with acceptance and validation of the patient's experience. Group skills' training is used to help patients develop less self-destructive and more adaptive means of coping with intolerable affects. These skills include awareness of emotions and reactions, interpersonal effectiveness, emotion regulation, and distress tolerance. Skills are then integrated into the individual treatment in problem situations, e.g. suicidal urges (Linehan, 1993).

- SFT (schema focused treatment) is a form of psychotherapy integrating cognitive therapy, behavior therapy, object relations, and gestalt therapy into one unified,

systematic approach to treatment. The focus in SFT is on changing maladaptive schemes that patients develop early in life and thereby improve emotion regulation skills. Change is achieved through a range of behavioral, cognitive, and experiential techniques that focus on (1) the therapeutic relationship, (2) daily life outside therapy (also through homework assignments), and (3) past (traumatic) experiences (Young et al., 2003). Psychomotor therapy (PMT) is part of the SFT treatment protocol.

[figure not shown]
In the Sinai Centrum, 2 “Zorgpaden” will be implemented in Fall2017:

“Zorgpad 1” with EMDR or ImRs (3-6 months) and Zorgpad 2” with EMDR-DBT or ImRs - SFT (9-12 months). Therapists need to be “adherent-to-the model”, which will be ascertained by regular supervision with audiovisual recordings based on the different theoretical psychotherapeutic principles and therapies are delivered by protocol. At this moment, there is no clear scientific evidence and criteria are not explicitly defined for the one or the other treatment, except that patients with PTSD without comorbid PD have to be indicated for “Zorgpad” 1.

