7.3 Other study parameters

The analyses on other study parameters, including the AUDIT will also be similar to the primary and secondary analyses. Safety data: Incidences (number and % of subjects with at least one occurrence) of key SAEs and AEs will be presented per group. For exploratory purposes, confidence intervals comparing both groups will be provided.

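### Between assessments, the only active SAE route is the therapist, and scheduled therapy covers far less of months 0-12 in the PTSD-only arms, so the exploratory safety comparison in 7.3 depends on unequal contact.

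*Combined protocol and SAP*

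**What the plan says.** **How events are found.** Section 6.2.1 sets the general rule: "All adverse events reported by the subject or observed by the investigator or his staff will be recorded". Section 6.2.2 adds a self-injury questionnaire at the regular assessments and, for SAEs needing medical care, says that "in between the assessments, therapists will report these incidents to the researchers at the weekly consultations". The same section states: "SAE's which will occur during the treatment and for which medical care is needed, will be reported to the accredited METC". Section 6.4 says SAEs are reported until the end of the study.

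**How long therapy lasts.** The Summary gives, for the BPD trial, "EMDR (3-6 months plus 6-9 months treatment pause) compared to integrated DBT-EMDR (12 months", and for the CPD trial, "ImRs (3-6 months plus 6-9 months treatment pause) compared to integrated ImRs-SFT (12 months". Section 3 says the PTSD treatments "consist of 12 to 18 sessions in maximum 6 months", while the integrated treatment "takes at least twice sessions per week, for the duration of one year". The care-pathway paragraph of section 3 gives 9-12 months for the integrated pathway. PTSD-only patients may start DBT or SFT after T4.

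**What is compared.** Section 7.3: "Incidences (number and % of subjects with at least one occurrence) of key SAEs and AEs will be presented per group". The next sentence adds between-group confidence intervals and labels them exploratory. No time window is given, and nothing limits the comparison to time observed equally in both arms.

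**The concern.** A therapist who sees a patient twice a week will hear of admissions, crises and other events that an unprompted patient may not report. The plan gives the arms very different amounts of that contact, and allocation determines the amount. A comparison of recorded events then mixes true risk with the chance of being recorded.

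The events most exposed to under-recording are those in the PTSD-only treatment pause. The Introduction itself raises worse end-state functioning and relapse after PTSD treatment alone, and 6.2.2 describes suicidality and self-injury as very common in this population. There is no DSMB (6.5), so 7.3 is the only planned between-arm look at safety.

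**Working it through.** **1. The plan's own figure.** Pause = 12 months minus 3-6 months of therapy = 6-9 months. This matches the Summary.

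**2. Coverage of months 0-12 by scheduled therapy.**
- PTSD-only: 3/12 to 6/12 = 25-50%.
- Integrated: 12/12 = 100%, or 9/12 = 75% at the short end of section 3.

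So 50-75% of PTSD-only follow-up to T4 lies outside the therapist route, against 0-25% of integrated follow-up.

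**3. What else operates outside therapy.**
- Subject or staff reports (6.2.1): all arms, but passive, so yield depends on contact. T1, T3 and FU can be completed online at home (5.3).
- Self-injury screener (Table 1): all arms, but confined to self-injury. Its T3 entry carries a different mark in the text available to me.
- T2 and T4 visits: all arms, but no AE/SAE enquiry is listed.
- Tic-P at T2, T4 and FU: may show hospital use, but is not linked to SAE reporting.
- End-of-treatment evaluation and monitored further treatment (section 3): relevant to PTSD-only patients, but not described as SAE collection.
- Extra contact for PTSD-only patients (5.3): three months after T3, and T3 is around month 9, so it falls at 9 + 3 = about month 12. It does not fill the pause, and no SAE enquiry is stated.
- Treating physician informing the study team of important changes: appears under withdrawal (5.4).

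None of these is a scheduled AE/SAE enquiry common to all arms.

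**4. Illustration of size.** The documents give no event rate and no capture rates. Assumed: equal true 12-month risk of 20% in both arms, constant hazard, capture 0.9 during therapy and *c* outside it. With *m* months of therapy:

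recorded risk = 1 − exp(−λ[0.9*m* + *c*(12 − *m*)]), where λ = −ln(0.8)/12 = 0.0186 per month.

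Worked case, integrated *m* = 12: 1 − exp(−0.0186 × 10.8) = 18.2%. PTSD-only *m* = 6, *c* = 0.3: 0.9 × 6 + 0.3 × 6 = 7.2, giving 12.5%. Gap 5.7 points.

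| Integrated / PTSD-only therapy (months) | gap, *c* = 0.3 | gap, *c* = 0.6 | gap, *c* = 0.8 |
|---|---|---|---|
| 12 / 4.5 | 7.1 | 3.5 | 1.1 |
| 12 / 6 | 5.7 | 2.8 | 0.9 |
| 9 / 6 | 2.9 | 1.4 | 0.5 |

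Gaps are percentage points of spurious excess in the integrated arm. At the extreme of 3 months of PTSD-only therapy against 12, with *c* = 0.3, the gap is 18.2 − 9.6 = 8.6 points. For scale, with 63 per arm, 0.5 to 7.1 points is 0.005 × 63 = 0.3 to 0.071 × 63 = 4.5 patients.

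**5. Effect on the intervals.** With 63 per arm, 20% true risk and 12 months of integrated therapy, a 95% Wald interval for the risk difference would exclude zero in 14% (PTSD-only 6 months) to 29% (3 months) of trials at *c* = 0.3, and in 6-7% at *c* = 0.7, instead of 5%. With 9 against 6 months and *c* = 0.3 it is 7.5%.

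**6. Check of the remedy.** If capture is the same with and without a therapist (*c* = 0.9), both arms record 18.2%. The apparent risk ratio is 1.00 and the false-difference rate returns to 5%.

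**The case against.** The strongest reply is that the PTSD-only arms are not left unobserved. AEs are recorded in all arms throughout the study, both arms attend T2 and T4, treatment drop-outs stay in follow-up (5.6), and there are an end-of-treatment evaluation, monitored further treatment and an extra contact. This stands. A reader might infer that ascertainment stops when EMDR or ImRs ends; it does not. What ends is scheduled therapist contact, and with it the only active route between assessments.

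A reader might also take the words in 6.2.2 limiting METC reports to SAEs during the treatment to mean that pause events are not reported. Sections 6.2.1 and 6.4 do not support that reading, although the wording could be clearer.

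Second, 7.3 labels the intervals exploratory, there is no safety hypothesis, and the CAPS-5 analysis does not use these data. This also stands and limits the severity. It does not make a contact-dependent comparison interpretable.

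Third, the sizes rest on assumed capture rates and durations. Section 3 puts T4 six months after the PTSD-only pathway ends, and Table 1 puts T2 around month 6, so the 6-month rows fit the schedule better than the 4.5-month row, and the gaps shrink. It is therefore too strong to say that the integrated arm will show more events; it will tend to if detection is lower outside therapy.

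Fourth, 7.3 names no window, and follow-up runs to 18 months. After T4, PTSD-only patients may start DBT or SFT, so the imbalance may reverse. This is correct, and is why the claim is confined to months 0-12.

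**Conclusion.** The point holds in limited form. Followed as written, the plan gives active between-assessment SAE ascertainment over 25-50% of months 0-12 in the PTSD-only arms and 75-100% in the integrated arms, with no common enquiry to offset it. Provided detection is lower outside therapy, the bias runs against the integrated arms. The size is not derivable from the documents. About 0.5 to 7 percentage points is an illustration at an assumed 20% true risk, 90% capture in therapy and 30-80% outside it.

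A reader might conclude that the trial's safety findings are invalid or that this must be resolved before the trial can proceed. The documents do not support that: the intervals are exploratory, other routes operate in every arm, and the primary efficacy analysis is untouched. Severity is moderate, and the correction is cheap.

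**What to change.** **In 6.2.** Add one identical short AE/SAE and hospital-admission question to the questionnaire sets already sent to all arms at T1, T2, T3, T4 and FU. Use the Tic-P at T2, T4 and FU as a cross-check for admissions. Record the source and date of every report. Reporting to the METC is unchanged.

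**In 7.3.** State the window. Base the exploratory between-group intervals for months 0-12 on events from the common enquiry. Alongside them, present all recorded SAEs from any source per group, including deaths and therapist reports, split by source and by on-therapy and pause time, with a statement that ascertainment of these differs by arm. Therapist-reported events should not be dropped: that would discard known SAEs, and the questionnaire alone would miss deaths and events in non-responders, with 25% drop-out expected (4.4).

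**Cost.** A few extra items and some wording, with no new visits. Self-reported events need checking against the file, which takes staff time. A common question equalises the method but does not guarantee equal response, so completion should be reported per arm. It should be in place before follow-up begins, because pause events not asked about at the time may not be recoverable.

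### Between assessments, section 6.2.2 relies on therapists to report SAEs, so ascertainment may differ between arms during the PTSD-only treatment pause and distort the exploratory safety comparison

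*Combined protocol and SAP*

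**What the plan says.** **SAE reporting.** Section 6.2.2 words its ethics-committee reporting sentence as "SAE's which will occur during the treatment and for which medical care is needed, will be reported to the accredited METC". For events outside the assessment visits it adds that "therapists will report these incidents to the researchers at the weekly consultations", and the researchers then notify the committee. The monitoring instrument it names is a self-injury questionnaire completed at the regular assessments. Section 6.4, by contrast, carries SAE reporting through to study end.

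**Exposure to therapy.** The Summary gives the A1 comparison as "EMDR (3-6 months plus 6-9 months treatment pause) compared to integrated DBT-EMDR (12 months", and A2 follows the same pattern. Section 3 gives integrated treatment at least two sessions a week for a year, but its care-pathway paragraph gives "EMDR-DBT or ImRs - SFT (9-12 months". These durations do not agree and should be reconciled.

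**Analysis.** Section 7.3 tabulates, per group, the number and percentage of subjects with at least one key SAE or AE. It adds that, for exploration, "confidence intervals comparing both groups will be provided". It makes no allowance for time on treatment or for differences in how events come to light.

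**The concern.** A therapist can report only what the therapist learns. In the integrated arms a treating therapist is in place for most or all of the first year. In the PTSD-only arms scheduled therapy stops after 3-6 months. If fewer events become known during the pause, the PTSD-only percentage falls for reasons unrelated to safety, and integrated treatment looks worse by comparison.

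This matters because section 6.2.2 itself describes suicidality and self-injury as very common in this population, and section 6.5 dispenses with a safety monitoring board. The recorded events are thus the main safety evidence, and the pause is a period in which deterioration could pass unseen.

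**Working it through.** **1. The plan's own figure.** Pause = 12 months minus PTSD treatment: 12 − 6 = 6 and 12 − 3 = 9 months. The stated 6-9 months is reproduced.

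**2. Share of the first year with scheduled therapy.**
- PTSD-only: 3/12 to 6/12 = 25-50%.
- Integrated: 9/12 to 12/12 = 75-100%.

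**3. Other capture in the documents, and what each leaves open.**
- Section 6.2.1 records every AE that is reported or observed during the study. It applies to all arms but is passive.
- Section 3 has crisis medication or intervention, and further treatment after EMDR or ImRs, monitored and documented. It applies to patients who receive such care and is not an enquiry put to everyone.
- Section 5.4 has the treating physician notify the team of important changes, without an SAE definition or schedule.
- Section 5.3 adds a contact for PTSD-only patients 3 months after T3. With T3 at about month 9, this is about month 12, the end of the pause.
- Table 1 schedules the self-injury questionnaire alike for all arms. Its name and stated source concern non-suicidal self-injury; the items are not reproduced.
- Table 1 schedules the Tic-P (health care use) at T0, T2, T4 and follow-up in all arms. The plan does not link it to SAE recording.
- Section 6.4 sets the reporting horizon but gives no method of asking.

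No section schedules a general SAE question at the assessments.

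**4. Illustrative size, expected events.** Assume the same true rate in both arms, constant over 12 months, full capture on treatment, and a share c captured off treatment. With M months of integrated and m months of PTSD-only treatment:

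ratio = (M + (12 − M)c) / (m + (12 − m)c)

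At c = 0.5:

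| | m = 3 | m = 6 |
|---|---|---|
| M = 12 | 12/7.5 = 1.60 | 12/9 = 1.33 |
| M = 9 | 10.5/7.5 = 1.40 | 10.5/9 = 1.17 |

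At c = 0.75 the range is 1.07 (11.25/10.5) to 1.23 (12/9.75). At c = 0.25 it is 1.30 (9.75/7.5) to 2.29 (12/5.25). At c = 1 the ratio is 1.00 when the durations differ only in therapy, as it should be.

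**5. Illustrative size, the statistic in section 7.3.** The percentage with at least one event, for true 12-month risk R, is 1 − (1 − R)^(k/12), where k is the numerator or denominator above. Take R = 10% (assumed), c = 0.5, M = 12 and 63 per arm (section 4.4).
- Integrated: 10.0%.
- PTSD-only: 1 − 0.9^(7.5/12) = 6.4% for m = 3; 1 − 0.9^(9/12) = 7.6% for m = 6.
- Risk ratio: 1.57 and 1.32. Difference: 3.6 and 2.4 points.
- Expected 95% interval, difference ± 1.96 × √[p(1 − p)/63 + q(1 − q)/63]: −5.9 to +13.2 and −7.5 to +12.3 points.

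With equal capture the difference is 0, with a half-width of 10.5 points. At 10% risk the interval includes zero for every capture share examined. The most extreme case, with no pause capture and m = 3, gives −1.0 to +15.8. With half of pause events captured, it includes zero at every assumed risk from 5% to 30%.

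**The case against.** The best defence is that the treatment-limited wording governs what goes to the ethics committee, not what is recorded. Recording follows section 6.2.1, which runs for the whole study, and section 6.4 extends SAE reporting to its end. The weekly consultations are meetings between therapists and researchers, not weekly patient contact, so loss of this route during the pause is an inference. Crisis care and further treatment are documented, and all arms share one assessment schedule with clinician interviews at T2 and T4. The comparison is labelled exploratory. After T4 the imbalance may even reverse, because PTSD-only patients may then start DBT or SFT.

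Most of this stands, and it rules out the stronger reading a reader might infer: that PTSD-only patients are under-recorded as a matter of fact, that the comparison is biased, and that the apparent ratio would be 2 to 4. That ratio needs zero capture in the pause and a full 12 months of integrated treatment (12/6 and 12/3). The other routes make zero capture implausible, and section 3 allows 9 months. The interval would wrongly exclude zero only under similarly extreme assumptions, such as 20% risk, 3 months of treatment and no pause capture (+3.2 to +25.9 points).

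The defence does not supply a scheduled SAE question. The remaining routes depend on a patient volunteering an event, on care being sought, or on someone noticing. The conflict between sections 6.2.2 and 6.4 also leaves sites without a clear window.

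**Conclusion.** The point holds as a risk of differential ascertainment, not as demonstrated bias. The therapist route in section 6.2.2 is available for a much smaller part of the first year in the PTSD-only arms, no uniform enquiry replaces it, and section 7.3 does not allow for the difference. The likely direction up to T4 is against integrated treatment.

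The size is unknown, because the documents give neither the SAE risk nor the share of events captured off treatment. With half captured, the apparent ratio is about 1.2-1.6 over 3-6 months of PTSD-only and 9-12 months of integrated treatment. At an assumed 10% risk the exploratory interval would still be expected to include zero, so a false safety signal is not the likely result. The practical loss is a less reliable comparison and possible blindness to events in the pause. The change should be made, since events not asked about alike in all arms cannot be reliably recovered later.

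**What to change.** 1. Reconcile the treatment-limited wording in section 6.2.2 with section 6.4, and state one SAE reporting window for all arms.
2. Add the same short SAE questions (hospital admission, suicide attempt, emergency care) to the existing T1, T2, T3, T4 and follow-up batteries in every arm. Keep the therapist route as a supplement.
3. In section 7.3, base the between-arm comparison on these systematically asked events from randomisation to T4, regardless of treatment status. Show T4 to follow-up separately, because access to treatment changes after T4.
4. Cross-check against the Tic-P at T2, T4 and follow-up.

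The cost is a few items and some wording, with no extra visits. It is not entirely free: T1, T3 and follow-up can be completed online at home, so someone must read the answers promptly. The 7-day limit (death or life-threatening events) and the 15-day limit (other SAEs) in section 6.2.2 run from first knowledge.
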